### **5.3.6 Patient-reported Outcomes**

The European Organization of Research and Treatment of Cancer Quality of Life Questionnaire (EORTC QLQ-C30) and the 20-item EORTC QLQ brain cancer module (EORTC QLQ-BN20) are self administered and are to be completed by the subject without the assistance of the investigational site personnel. All questionnaires should be completed if possible before any other study procedures are conducted at the study visit. If a subject anticipates that he/she will be unable to complete the questionnaire on Day 1 of a cycle visit, the questionnaire may be completed within 3 days prior to the schedule Day 1 visit provided there is another reason for the subject to be in the clinic prior to the assessment time point. If the questionnaire cannot be completed within 3 days prior to dosing Day 1, subjects will be allowed to complete the questionnaire following the infusion.

### **5.3.6.1 EORTC QLQ-C30 and EORTC QLQ-BN20**

The EORTC QLQ-C30 is a 30-item self-administered questionnaire that consists of 5 functional scales (physical, role, cognitive, emotional and social functioning), 3 symptom scales (fatigue, pain, and nausea, and vomiting), and a number of single items assessing additional symptoms commonly reported by cancer patients (eg, dyspnea, loss of appetite, insomnia, constipation, diarrhea, and financial difficulties). In addition, a disease-specific 20-item, self-administered questionnaire for brain cancer (EORTC QLQ-BN20) was developed comprising both multi-item and single-item measures of brain-cancer-associated symptoms (eg, fatigue and sleep disturbance, emotional, physical, role, and social functioning, and global quality of life) (Osoba et al, 1996) to be used in conjunction with the EORTC QLQ-C30.

Subjects will be asked to rate each item on a 4-point scale (eg, for the preceding week, they will be asked, “Have you had pain?” and will then be asked to choose among “Not at all, a little, quite a bit, or very much.”). Each of the multi-item scales includes a different set of items - no item occurs in more than 1 scale. All of the scales and single-item measures range in score from 0 to 100. Scores are then transformed onto a 0-100-point scale. For the 5 functional scales, higher scores represent better level of functioning. For the symptom scales, higher scores represent worse symptoms. (Aronson et al, 1993).

### **5.3.7 Disease Evaluation and Methods**

Tumor measurements and assessments will be based on *Updated Response Assessment Criteria of High Grade Gliomas- Neuro-Oncology Working Group* (Wen et al, 2010) (see [Appendix 4](#) and [Appendix 5](#)) and will be performed as specified in [Table 5.2-1](#) and [Table 5.2-2](#). Tumor assessments include an MRI scan of the brain. Additional tumor assessments may be performed at the discretion of the investigator or according to institutional practice. In subjects who achieve a complete or partial response to treatment, tumor measurements will be repeated at least 4 weeks later using the same imaging tests. The same tumor assessment method should be used throughout the treatment period. It is recommended to use the same MRI scanner or one with same magnet strength throughout the assessments.

Blinded central independent imaging review of response and disease progression will be utilized. Details of study-specific procedures for collection and shipment of images will be provided in a separate manual.

## **Measurability of Tumor Lesions**

Measurable disease is defined as bidimensionally contrast enhancing lesions with clearly defined margins by MRI scan, with two perpendicular diameters of at least 10 mm, visible on two or more axial slices that are preferably, at most, 5 mm apart with 0-mm skip. In the event the MRI is performed with thicker slices, the size of a measurable lesion at baseline should be two times the slice thickness. In the event there are interslice gaps, this also needs to be considered in determining the size of measurable lesions at baseline. Measurement of tumor around a cyst or surgical cavity represents a particularly difficult challenge. In general, such lesions should be considered nonmeasurable unless there is a nodular component measuring 10 mm in diameter. The cystic or surgical cavity should not be measured in determining response. (Wen et al, 2010).

Nonmeasurable disease is defined as either unidimensionally measurable lesions, masses with margins not clearly defined, or lesions with maximal perpendicular diameters less than 10 mm. (Wen et al, 2010).

## **Number of Lesions**

If there are multiple contrast-enhancing lesions, a minimum of the two largest lesions should be measured, and the sum of the products of the perpendicular diameters of these lesions should be determined. A maximum of five of the largest lesions may be measured; the largest enlarging lesion(s) should be selected, with emphasis placed on lesions that allow reproducible repeated measurements.

For patients with recurrent disease who have multiple lesions of which only one or two are increasing in size, the enlarging lesions should be considered the target lesions for evaluation of response. The other lesions will be considered nontarget lesions and should also be recorded. Rarely, unequivocal progression of a nontarget lesion requiring discontinuation of therapy or development of a new contrast enhancing lesion may occur, even in the setting of stable disease or partial response in the target lesions. These changes would qualify as progression.

## **Evaluation of Overall Response**

Table 5.3.7-1 provides overall responses for possible combinations of tumor responses.

**Table 5.3.7-1 Evaluation of Overall Response**

Criterion	Response Category			
	CR	PR	SD	PD
T1 gadolinium enhancing disease	None	≥50% ↓	< 50% ↓but < 25% ↑	≥25% ↑ a
T2/FLAIR	Stable or ↓	Stable or ↓	Stable or ↓	↑ a
New lesion	None	None	None	Present a
Corticosteroids	None	Stable or ↓	Stable or ↓	NA †
Clinical status	Stable or ↑	Stable or ↑	Stable or ↑	↓ a
Requirement for response	All	All	All	Any a

↓ = decreased, ↑ = increased ; CR = complete response, FLAIR = fluid attenuated inversion recovery; NA = not applicable; PD = progressive disease; PR = partial response, SD = stable disease,

a Progression occurs when this criterion is present

Source: Wen PY, Macdonald DR, Reardon DA, Cloughesy TF, Sorenson AG, Galanis E, et al. Updated Response Assessment Criteria for High-Grade Gliomas: Response Assessment in Neuro-Oncology Working Group; J Clin Oncol. 2010Apr10;28(11):1963-72.

### 5.3.8 Estimate of Volume of Blood to Be Collected

No more than 35 mL of blood will be drawn on a per-day basis across all tests combined on days in which blood is collected. The estimated volume of blood to be collected during the first treatment cycle is 115 mL whereas 30 mL will be collected during every subsequent cycle. The total volume to be collected for all subjects will depend on the number of cycles administered and the length of follow-up.

## 6 Assessment of Safety

### 6.1 Safety Parameters

#### 6.1.1 Adverse Events

The ICH Guideline for Good Clinical Practice E6(R1) defines an AE as:

Any untoward medical occurrence in a patient or clinical investigation subject administered a pharmaceutical product and which does not necessarily have a causal

relationship with this treatment. An AE can therefore be any unfavorable and unintended sign (including an abnormal laboratory finding), symptom, or disease temporally associated with the use of a medicinal product, whether or not considered related to the medicinal product

An AE includes, but is not limited to any clinically significant worsening of a subject's pre-existing condition. An abnormal laboratory finding (including ECG finding) that requires an action or intervention by the investigator, or a finding judged by the investigator to represent a change beyond the range of normal physiologic fluctuation, should be reported as an AE.

Adverse events may be treatment emergent (ie, occurring after initial receipt of investigational product) or nontreatment emergent. A nontreatment-emergent AE is any new sign or symptom, disease, or other untoward medical event that begins after written informed consent has been obtained but before the subject has received investigational product.

Elective treatment or surgery or preplanned treatment or surgery (that was scheduled prior to the subject being enrolled into the study) for a documented pre-existing condition that did not worsen from baseline is not considered an AE (serious or nonserious).

### **6.1.2 Serious Adverse Events**

A serious adverse event (SAE) is any AE that:

- Results in death
- Is immediately life-threatening  

This term refers to an event in which the subject was at risk of death at the time of the event; it does not refer to an event that may have led to death.
- Requires inpatient hospitalization or prolongation of existing hospitalization  

In general, hospitalization signifies that the subject has been detained (usually involving at least an overnight stay) at the hospital or emergency ward for observation and/or treatment that would not have been appropriate in an outpatient setting.
- Results in persistent or significant disability/incapacity  

The term disability means a substantial disruption of a person's ability to conduct normal life functions.
- Is a congenital anomaly/birth defect in offspring of the subject

- Is an important medical event that may jeopardize the subject or may require medical intervention to prevent one of the outcomes listed above.

Medical or scientific judgment should be exercised in deciding whether expedited reporting is appropriate in this situation. Examples of medically important events are intensive treatment in an emergency room or at home for allergic bronchospasm, blood dyscrasias, or convulsions that do not result in hospitalizations; or development of drug dependency or drug abuse.

### 6.1.3 Other Events of Special Interest

#### 6.1.3.1 Hepatic Function Abnormality

A hepatic function abnormality of special interest to the sponsor is defined as any increase in ALT or AST to greater than 3× ULN **and concurrent** increase in bilirubin to greater than 2× ULN. Concurrent findings are those that derive from a single blood draw or from separate blood draws taken within 8 days of each other. Follow-up investigations and inquiries will be initiated promptly by the investigational site to determine whether the findings are reproducible and/or whether there is objective evidence that clearly supports causation by a disease (eg, cholelithiasis and bile duct obstruction with distended gallbladder or an agent other than the investigational product).

#### 6.1.3.2 Infusion Reaction

Any infusion related reaction resulting in permanent discontinuation of investigational product must be reported *within 24 hours of knowledge of the event* to MedImmune Patient Safety or designee using the Fax Notification Form (see Section 6.4.2.2 for contact information)

## 6.2 Assessment of Safety Parameters

### 6.2.1 Assessment of Severity

Assessment of severity is one of the responsibilities of the investigator in the evaluation of AEs and SAEs. Severity will be graded according to the NCI CTCAE v4.03 as provided in [Appendix 2](#). The determination of severity for all other events not listed in the CTCAE should be made by the investigator based upon medical judgment and the severity categories of Grade 1 to 5 as defined below.

An event that is usually transient and may require only minimal treatment or therapeutic intervention. The event does not generally interfere with usual activities of daily living.

Grade 2 (moderate)

An event that is usually alleviated with additional specific therapeutic intervention. The event interferes with usual activities of daily living, causing discomfort but poses no significant or permanent risk of harm to the subject.

Grade 3 (severe)

An event that requires intensive therapeutic intervention. The event interrupts usual activities of daily living, or significantly affects the clinical status of the subject.

Grade 4 (life threatening)

An event, and/or its immediate sequelae, that is associated with an imminent risk of death or with physical or mental disabilities that affect or limit the ability of the subject to perform activities of daily living (eating, ambulation, toileting, etc).

Grade 5 (fatal)

Death (loss of life) as a result of an event.

It is important to distinguish between serious criteria and severity of an AE. Severity is a measure of intensity whereas seriousness is defined by the criteria in Section 6.1.2. A Grade 3 AE need not necessarily be considered an SAE. For example, a Grade 3 headache that persists for several hours may not meet the regulatory definition of an SAE and would be considered a nonserious event, whereas a Grade 2 seizure resulting in a hospital admission would be considered an SAE.

## **6.2.2 Assessment of Relationship**

### **6.2.2.1 Relationship to Investigational Product**

The investigator is required to provide an assessment of relationship of AEs and SAEs to the investigational product.

An event will be considered “not related” to use of the investigational product if any of the following are met:

- An unreasonable temporal relationship between administration of the investigational product and the onset of the event (eg, the event occurred either before or too long after administration of the investigational product for it to be considered product-related)
- A causal relationship between the investigational product and the event is biologically implausible (eg, death as a passenger in an automobile accident)
- A clearly more likely alternative explanation for the event is present (eg, typical adverse reaction to a concomitant drug and/or typical disease-related event)

Individual AE/SAE reports will be considered “related” to use of the investigational product if the “not related” criteria are not met.

“Associated with the use of the drug” means that there is “a reasonable possibility” that the event may have been caused by the product under investigation (ie, there are facts, evidence, or arguments to suggest possible causation).

#### **6.2.2.2 Relationship to Protocol Procedures**

The investigator is also required to provide an assessment of relationship of SAEs to protocol procedures on the SAE Report Form. This includes nontreatment-emergent SAEs (ie, SAEs that occur prior to the administration of investigational product) as well as treatment-emergent SAEs. A protocol-related SAE may occur as a result of a procedure or intervention required during the study (eg, blood collection, washout of an existing medication). The following guidelines should be used by investigators to assess the relationship of SAEs to the protocol:

**Protocol related:** The event occurred due to a procedure/intervention that was described in the protocol for which there is no alternative etiology present in the subject’s medical record.

**Not protocol related:** The event is related to an etiology other than the procedure/ intervention that was described in the protocol (the alternative etiology must be documented in the subject’s medical record).

## **6.3 Recording of Safety Parameters**

### **6.3.1 Recording of Adverse Events and Serious Adverse Events**

Adverse events will be recorded on the CRF using a recognized medical term or diagnosis that accurately reflects the event. Adverse events will be assessed by the investigator for severity, relationship to the investigational product, possible etiologies, and whether the event meets criteria of an SAE and therefore requires immediate notification to MedImmune Patient Safety. See Section 6.1.2 for the definition of SAEs, and Section 6.2.1 and Section 6.2.2 for guidelines for assessment of severity and relationship, respectively. If an AE evolves into a condition that meets the regulatory definition of “serious,” it will be reported on the SAE Report Form.

### **6.3.2 Recording of Other Events of Special Interest**

Special interest events will be recorded on the eCRF using recognized medical terms or diagnosis that accurately reflects the event in the same manner all AEs and SAEs are captured as described in Section 6.3.1. See Section 6.1.3 for definitions of events of special interest and Section 6.4.4 for additional reporting requirements.

#### **Hepatic Function Abnormality**

Events of hepatic function abnormality (as defined in Section 6.1.3.1) should be recorded according to the definitions of AE and SAE (Section 6.1.1 and Section 6.1.2, respectively):

- If an event of hepatic function abnormality is considered to be related to a pre-existing condition and does not represent a worsening of this condition and/or is considered to be within the range of normal physiological fluctuation for the subject, the event does not meet the definition of an AE and does not need to be recorded as such.
- If a definitive diagnosis for an underlying condition unrelated to the investigational product is established for an event of hepatic function abnormality, the diagnosis should be recorded as an AE/SAE per Section 6.3.1.
- If no definitive diagnosis is determined for an event of hepatic function abnormality, the term “hepatic function abnormal” should be used to report the AE/SAE per Section 6.3.1.

## **6.4 Reporting Requirements for Safety Parameters**

### **6.4.1 Study Reporting Period and Follow-up for Adverse Events**

The reporting period for AEs is the period immediately following the time that written informed consent is obtained through 90 days post the last dose of treatment or until the subject begins another anticancer therapy, whichever occurs first. New (nonserious) AEs that start after the reporting period will not be collected.

All AEs will be followed to resolution through the end of subject participation in the study, even if the date extends beyond the reporting period.

### **6.4.2 Reporting of Serious Adverse Events**

#### **6.4.2.1 Study Reporting Period and Follow-up for Serious Adverse Events**

The reporting period for nontreatment and treatment-emergent SAEs is the period immediately following the time that written informed consent is obtained through 90 days post the subject's last dose of treatment or until the subject begins another anticancer therapy, whichever occurs first. The reporting period for protocol-related SAEs (see Section 6.2.2.2) is the period immediately following the time that written informed consent is obtained through the end of subject participation in the study. After submitting an initial SAE report for a subject (to MedImmune Patient Safety), the investigator is required to follow the subject proactively and provide further information on the subject's condition to MedImmune Patient Safety or designee.

At any time after the reporting period if an investigator or qualified designee becomes aware of an SAE that is suspected by the investigator or qualified designee to be related to investigational product, the event must be reported to MedImmune Patient Safety.

The investigator is responsible for following all SAEs until resolution, until the subject returns to baseline status, or until the condition has stabilized with the expectation that it will remain chronic, even if this extends beyond study participation.

#### **6.4.2.2 Notifying the Sponsor of Serious Adverse Events**

**Within 24 hours of identifying an SAE, regardless of the presumed relationship to the investigational product, the investigator or qualified designee must complete the SAE Report Form and fax it to MedImmune Patient Safety or designee.**

MedImmune or designee

Patient Safety  
MedImmune  
[name]  
[name]  
[contact]

The sponsor is responsible for reporting certain SAEs as expedited safety reports to applicable regulatory authorities, ethics committees, and participating investigators, in accordance with ICH Guidelines and/or local regulatory requirements (see Section [6.4.2.3](#)). The sponsor may be required to report certain SAEs to regulatory authorities within 7 calendar days of being notified about the event; therefore, it is important that investigators submit additional information requested by the sponsor as soon as it becomes available.

Investigators should provide all available information at the time of SAE Report Form completion. Investigators should not wait to collect additional information to fully document the event before notifying MedImmune Patient Safety of an SAE. When additional information becomes available, investigators should submit a follow-up SAE Report Form (separate from the initial report form) with the new information. Any follow-up information to an SAE also needs to be provided to MedImmune Patient Safety within 24 hours of learning of the new information.

#### **6.4.2.3 Safety Reporting to Investigators, Institutional Review Boards or Independent Ethics Committees, and Regulatory Authorities**

The sponsor is responsible for reporting all applicable SAEs to regulatory authorities, investigators, and IRBs/IECs, as applicable, in accordance with national regulations in the countries where the study is conducted. The sponsor will also prepare an expedited report for other safety issues where these might materially alter the current benefit-risk assessment of an investigational product or that would be sufficient to consider changes in the administration of the investigational product or in the overall conduct of the study.

The sponsor will prepare an expedited report for all SAEs that are unexpected and potentially related to the investigational product, and copies will be distributed to all concerned regulatory authorities, investigator(s), and IRBs/IECs according to applicable laws and regulations. The investigational site also will forward a copy of all expedited reports to the site's applicable IRB/IEC. Investigators must also submit safety information provided by the sponsor to the IRB/IEC as detailed in Section 10.1 and Section 10.2.

### **6.4.3 Other Events Requiring Immediate Reporting**

#### **6.4.3.1 Overdose**

An overdose is defined as a subject receiving a dose of investigational product in excess of that specified in the Investigator's Brochure, unless otherwise specified in this protocol.

Any overdose of a study subject with the investigational product, with or without associated AEs/SAEs, is required to be reported within 24 hours of knowledge of the event to MedImmune Patient Safety or designee using the Fax Notification Form (see Section 6.4.2.2 for contact information). If the overdose results in an AE, the AE must also be recorded on the AE CRF (see Section 6.3.1). Overdose does not automatically make an AE serious, but if the consequences of the overdose are serious, for example death or hospitalization, the event is serious and must be reported as an SAE (see Section 6.3.1 and Section 6.4.2).

#### **6.4.3.2 Hepatic Function Abnormality**

Hepatic function abnormality (as defined in Section 6.1.3.1) in a study subject, with or without associated clinical manifestations, is required to be reported as "hepatic function abnormal" within 24 hours of knowledge of the event to MedImmune Patient Safety using the Safety Fax Notification Form (see Section 6.4.2.2 for contact information), unless a definitive underlying diagnosis for the abnormality (eg, cholelithiasis and bile duct obstruction) that is unrelated to investigational product has been confirmed.

- If the definitive underlying diagnosis for the abnormality has been established and is unrelated to investigational product, the decision to continue dosing of the study subject will be based on the clinical judgment of the investigator.
- If no definitive underlying diagnosis for the abnormality is established, dosing of the study subject must be interrupted immediately. Follow-up investigations and inquiries must be initiated by the investigational site without delay.

Each reported event of hepatic function abnormality will be followed by the investigator and evaluated by the sponsor. If the etiology of the event remains unconfirmed and/or is considered related to investigational product (see Section 6.2.2.1), a prompt cumulative review of safety data and the circumstances of the event in question will be conducted and assessed by the MedImmune SMC (see Section 6.5) to determine whether continued dosing of current study subjects and/or study entry should be interrupted, whether the protocol will be modified, or whether the study will be discontinued permanently. Review and approval by the MedImmune SMC is required for resumption of subject dosing or study entry in the event that the study is interrupted. Where applicable, regulatory authorities and IRBs/IECs will be notified of any actions taken with the study.

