### 3.3 Study Stopping Criteria

If any of the following occur, administration of investigational product will be stopped and no additional subjects will be entered into the study:

- 1) Death in any subject in which the cause of death is assessed as related to investigational product
- 2) Anaphylactic reaction to investigational product in any subject
- 3) Other events that, in the judgement of the medical monitor, are deemed serious enough to warrant immediate review by the MedImmune Safety Monitoring Committee (SMC)
- 4) A DLT rate greater than 30% in the first 15 subjects enrolled in the study (see Section 4.5.4.2)

If any of the above-listed events occurs, a prompt cumulative review of safety data and the circumstances of the event in question will be conducted (see Section 6.5) to determine whether dosing and study entry should be resumed, whether the protocol will be modified, or whether the study will be discontinued permanently. Review and approval by the MedImmune SMC are required for resumption of the study in the event the study is

interrupted because of 1 of the above-listed events. Where applicable, regulatory authorities and Institutional Review Boards (IRB)/Independent Ethics Committees (IEC) will be notified of any study actions taken.

Any subjects who have already received investigational product and are currently in the study at the time study stopping criteria are met will continue to be followed by the investigator for safety.

Withdrawal criteria for individual subjects are provided in Section [4.2.3](#).

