**Table 4.5.4.3-1 MEDI-575 Dose Modification Table**

Hematologic or Nonhematologic Toxicity Attributable to MEDI-575 alone	Dose Modification of MEDI-575
≤ Grade 1	None
Grade 2	
MEDI-575 may be withheld for up to 21 days until resolution to ≤ Grade 1 or baseline and resume at current dose level after discussion with the medical monitor. If subjects experience Grade 2 toxicities that are clinically manageable MEDI-575 may be continued at the current dose and schedule following consultation with the medical monitor. Grade 2 electrolyte abnormalities that can be alleviated through electrolyte replacement do not require dose delay or reduction.
 
Discontinue MEDI-575 if withheld for > 21 days without resolution of toxicity to ≤ Grade 1 or baseline unless clearly attributable to another cause such as disease progression, concomitant therapy or accident.

Grade 3 or 4	
First Occurrence:
 
Withhold MEDI-575 for up to 21 days until resolution to ≤ Grade 1 or baseline. Restart MEDI-575 at 50% of the starting dose.
 
Subjects who experience Grade 3 or Grade 4 laboratory abnormalities or AEs without associated clinical findings that resolve to ≤ Grade 1 or baseline within 21 days will not require dose modification or discontinuation
 
Discontinue MEDI-575 if withheld for > 21 days without resolution of toxicity to ≤ Grade 1 or baseline.
 
Second Occurrence:
 
Discontinue MEDI-575.

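### After an unexplained Grade 3 or 4 combined liver abnormality, Table 4.5.4.3-1 and Section 6.4.3.2 do not agree on when the individual subject may restart MEDI-575

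*Protocol*

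**What the plan says.** Section 6.1.3.1 defines the event by laboratory values alone: ALT or AST above 3× ULN with a concurrent bilirubin above 2× ULN. On timing it adds: "Concurrent findings are those that derive from a single blood draw or from separate blood draws taken within 8 days of each other".

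Section 6.4.3.2 then sets out the handling:

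- The event is reported within 24 hours, with or without clinical signs, unless an unrelated diagnosis has been confirmed.
- If there is a definitive unrelated diagnosis, the investigator decides on further dosing.
- Otherwise: "If no definitive underlying diagnosis for the abnormality is established, dosing of the study subject must be interrupted immediately".
- The sponsor evaluates each reported event. A prompt cumulative safety review, assessed by the SMC, follows under this condition: "If the etiology of the event remains unconfirmed and/or is considered related to investigational product".
- The only sentence on resumption says that review and "approval by the MedImmune SMC is required for resumption of subject dosing or study entry in the event that the study is interrupted".

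Table 4.5.4.3-1 gives restart rules by grade:

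- **Grade 2:** after resolution, "resume at current dose level after discussion with the medical monitor".
- **Grade 3 or 4, first occurrence:** withhold for up to 21 days until resolution to Grade 1 or baseline, then "Restart MEDI-575 at 50% of the starting dose". Laboratory abnormalities or AEs without clinical findings that resolve within 21 days need no dose modification.

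The table does not mention Section 6.4.3.2, and Section 6.4.3.2 does not mention the table.

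**The concern.** An unexplained rise in transaminases and bilirubin together is the situation that Section 6.4.3.2 was written to control. It stops the subject's dosing and starts an assessment of cause, but it does not make that assessment a condition of the same subject's next dose. The Grade 3/4 row of the dose table does contain a complete restart rule, and that rule depends on resolution and not on cause. A site could follow the row in good faith and re-expose a subject while the SMC-assessed review is still open. What is at stake is the safety of that subject. The efficacy result is not at issue.

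**Working it through.** The protocol gives no figure to reproduce. The check is a comparison of texts, followed by a timing illustration.

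**1. Can an unexplained event reach the table?** Three provisions point that way.

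- The opening text of Section 4.5.4.3 applies the table to toxicities that cannot be put down to another cause, after the first cycle.
- Section 6.3.2 begins "If no definitive diagnosis is determined for an event of hepatic function abnormality, the term" and goes on to prescribe a generic label under which the event is reported as an AE or SAE.
- Section 6.2.2.1 treats an event as related unless one of its criteria for not related is met.

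One provision points the other way: the table's column heading limits it to toxicity due to MEDI-575 by itself. The event can therefore reach the table, but the text does not settle that it must.

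**2. What does the table require before restart?** In the Grade 3/4 row, only resolution within 21 days. No medical monitor, sponsor or SMC step appears in that row. The event is defined by laboratory values, so a case without clinical findings can also fall under the exception that needs no dose modification. The Grade 2 row differs, because it requires discussion with the medical monitor.

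**3. What does Section 6.4.3.2 require before restart?** For one held subject, nothing explicit. SMC approval is tied to interruption of the study. Section 3.3 does not list a single hepatic abnormality as study-stopping. Its closest route is criterion 3, "Other events that, in the judgement of the medical monitor, are deemed serious enough to warrant immediate review", which depends on that judgement being made. The SMC review can itself lead to an interruption, and the approval requirement would then apply. The decisions listed for that review concern interrupting, modifying or ending. Release of the held subject is not among them.

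**4. The two readings side by side.**

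- *The table governs.* A Grade 3/4 subject restarts on resolution, and nothing ties the restart to the work-up or to the SMC review.
- *Section 6.4.3.2 governs, and the hold lasts while no diagnosis exists.* A subject whose cause is never found cannot restart, although the table would restart that subject.

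The readings give opposite answers for the same subject, and the text does not choose between them.

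**5. Timing illustration.** Without delays, Cycle k Day 1 falls on Day 1 + 21(k − 1), so Cycle 3 Day 1 is 1 + 42 = Day 43. Cycle 3 is used because Section 4.5.4.3 applies the table after the first cycle. Suppose the event is found on pre-infusion chemistry that day and the dose is held.

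- The report is due within 24 hours, by Day 44.
- Resolution time is not in the protocol; 7 to 21 days is assumed. The table would then allow restart between 43 + 7 = Day 50 and 43 + 21 = Day 64.
- From the report deadline that is 50 − 44 = 6 days to 64 − 44 = 20 days.
- The minimum of 21 days between doses is met: the last dose was on Day 22, and 50 − 22 = 28.

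Section 6.4.3.2 asks for promptness but sets no day limit. Under these assumptions, a review still open 6 to 20 days after the report could be overtaken by the restart rule.

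**The case against.** The strongest reply is that Section 6.4.3.2 already answers the question. Its two bullets are alternatives, so while no diagnosis exists the duty to interrupt continues. A specific mandatory rule for a defined event is ordinarily read ahead of a general grade table. The column heading supports this, since an event of unknown cause has not been attributed to MEDI-575 alone, and the related-by-default rule in Section 6.2.2.1 is a reporting convention. The statement that certain laboratory abnormalities need no dose modification does not cancel an interruption required elsewhere.

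There is also real oversight: 24-hour reporting, sponsor evaluation, SMC-assessed review, sponsor agreement on withheld doses (Section 4.5.2), the medical monitor's ability to bar further dosing (Section 4.2.3) and the SMC's power to suspend dosing (Section 6.5). A gap of 6 to 20 days is compatible with a prompt review.

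Most of this stands, and it limits the point. A reader might infer that the protocol permits re-dosing before the cause is known. It does not say so; that would be an inference from silence in one section and general wording in another. A reader might also extend the point to Grade 2. Restart there already needs medical monitor discussion, and any argument about continued Grade 2 dosing depends on CTCAE limits that the protocol does not reproduce. Finally, a reader might infer that a long review forces discontinuation at 21 days. The table discontinues after 21 days only where the toxicity has not resolved.

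The reply does not remove the conflict. None of the safeguards says that an individual restart waits for the assessment of cause, and the reading that keeps the hold contradicts the table for a subject whose cause is never found.

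**Conclusion.** The point holds as a conflict between two sections, confined to events that meet Section 6.1.3.1, are Grade 3 or 4 and have no definitive unrelated diagnosis. For these, Table 4.5.4.3-1 can be read to allow restart on resolution within 21 days, at half dose or with no required change. Section 6.4.3.2 requires a hold and an SMC-assessed review without making SMC approval a condition of that subject's restart.

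The size is small. The protocol gives no event rate and none is claimed. How many qualifying events are Grade 3 or 4 cannot be derived, because the grade limits are not reproduced. The 6 to 20 days rest on the assumed resolution time. The primary endpoint and sample size are unaffected. Harm would require a site to apply the general table over the specific rule and the sponsor, already notified, not to step in. This is a cheap improvement worth making.

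**What to change.** Make two additions in the next amendment:

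1. In Table 4.5.4.3-1: *Events meeting Section 6.1.3.1 without a definitive unrelated diagnosis follow Section 6.4.3.2, regardless of grade.*
2. In Section 6.4.3.2: *A subject whose dosing is interrupted under this section may resume only after a definitive unrelated diagnosis is established, or after the SMC, on completing the assessment required here, approves that subject's resumption.*

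The second sentence should require approval. Mere completion of the assessment would let an unfavourable review satisfy the condition. The 21-day withholding rule can stay as it is.

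The cost is one table line and one sentence, with no new procedure or review body. The downside is a longer dose delay for a few subjects.
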